## 4.1. Dose and Treatment Schedule

Approximately 90 subjects are planned to be enrolled. Oral doses of EDP-938 or placebo, will be administered OD. Initial doses are planned to

be 5 mg/kg in each age group:

- Group 1 (Ages  $\geq 6$  to  $\leq 36$  months);
- Group 2 (Ages  $\geq$  28 days to <6 months);

Varying age-appropriate volumes of a fixed concentration (**Constitution**) of EDP-938 or placebo will be administered to achieve the intended dose in each pediatric patient.

Subjects who meet all of the inclusion criteria and none of the exclusion criteria will be eligible to enter the study and will be randomized 2:1 (Part 1) or 4:1 (Part 2) to EDP-938:placebo.

The study design is shown in Figure 1.

## Part 1

Enrollment will begin simultaneously with Cohort 1 Age Group 1 and Cohort 1 Age Group 2. When at least 9 subjects have been randomized in Cohort 1, for each age group, the SSC will review available blinded data, including at least safety and PK data, and will determine dosing for Part 1 Cohort 2 for each age group. The SSC will meet as required to review emerging safety and PK data to support dose decision and initiation of Cohort 2. Enrollment in Cohort 1 age groups will continue until 12 subjects have been enrolled.

Cohort 1 Age Group 1 will include subjects who may be hospitalized or non-hospitalized at enrollment. Cohort 1 Age Group 2 will include subjects who are hospitalized at enrollment.

Clinical Study Protocol	
EDP 938-201	

Cohort 2 for both age groups will include subjects who may be hospitalized or non-hospitalized at enrollment.

Additional Part 1 cohorts may be added, as deemed necessary by the SSC.

## Part 2

Both age groups will include subjects who may be hospitalized or non-hospitalized at enrollment. The start of dosing for each age group will be contingent upon at least 6 subjects in that age group being exposed to EDP-938 in Part 1 Cohort 2 and will be based on SSC recommendations. After completion of dosing in the Part 2 cohort, the SSC will review available blinded data, including at least safety and PK data, in that age group. Twenty subjects are planned for each age group, but additional subjects may be enrolled based on SSC recommendations to allow a sufficient number of subjects to determine doses for both age ranges.

Additional Part 2 cohorts may be added, as deemed necessary by the SSC.

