## 4.4. Rationale for Study Design

This is the first study investigating the use of EDP-938 in pediatric patients. Based on current RSV guidance documents, the pathophysiology of RSV disease is believed to be different between adults and pediatric patients. Therefore, methods of efficacy extrapolation from adults to pediatric patients may not be appropriate. Thus, the goal of this first EDP-938 pediatric clinical trial is to evaluate the safety, tolerability, PK, clinical outcomes, and antiviral activity of
EDP-938 in pediatric patients  $\geq$ 28 days to  $\leq$ 36 months of age who are infected with RSV and who may be hospitalized or non-hospitalized. This study is designed to support dose selection within each age group/cohort and to provide data to support dose selection for future pediatric clinical trials.

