#### 4.4.1. Justification of Study Design, Endpoints, and Subject Population

Despite the significant medical need, there is no vaccine or highly effective treatment currently available for RSV in children or adults. Currently, only 2 drugs are approved for treatment or prevention of RSV lower respiratory tract infection in pediatric patients: aerosolized ribavirin (a nucleoside analog) for treatment and palivizumab (a monoclonal antibody that targets the RSV fusion protein) for the prevention of serious lower respiratory tract disease caused by RSV in high risk children. However, analyses performed subsequent to the approval of aerosolized ribavirin suggest that it failed to impart any clinically significant benefits (Randolph & Wang, 1996), and currently it is not recommended for routine treatment of RSV (Piedimonte & Perez, 2014). There are also concerns about the toxicity, teratogenicity, and high cost of inhaled ribavirin (Chemaly, Aitken, Wolfe, Jain, & Boeckh, 2016). Current management of RSV bronchiolitis remains mostly supportive care such as oxygen for hypoxemia and intravenous fluids for dehydration. Consequently, clinicians have no safe and highly effective treatment for RSV infection, which is an issue of significant concern for those providing medical care for pediatric patients at risk of severe RSV disease.

This Phase 2 study aims to evaluate the safety, tolerability, PK, and antiviral activity of EDP-938 administered orally in pediatric patients  $\geq$ 28 days to  $\leq$ 36 months of age who are infected with RSV. The design of the study (randomized, double-blind, placebo-controlled, dose-ranging) is consistent with recent RSV guidance from regulatory agencies (EMA; FDA).

While this initial Phase 2 trial should identify the optimal dose and treatment duration of EDP-938 with regard to PK, safety, and antiviral activity in children aged 28 days to 36 months, we will also be exploring the use of instruments for RSV signs and symptoms that may be relevant to a later stage of EDP-938 development in the pediatric population.

The study will be conducted in 2 parts. In Part 1, the primary endpoints will be safety, tolerability, and PK. In Part 2, the primary endpoint will be antiviral activity. In Part 1, subjects will be randomized 2:1 to EDP-938:placebo. The SSC will make recommendations to determine dose selection and cohort progression in Part 1 and Part 2.

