Safety data on EDP-938 available to date supports the enrollment of both age groups, 6 months to 36 months and 28 days to less than 6 months. At least 2 dosing cohorts will be evaluated in Part 1. Part 1 Cohort 1 of both age groups will evaluate an initially selected dose of the which is anticipated to yield exposures that are safe and efficacious. As these exposures are predicted based on modeling and simulation using adult data (Section 4.4.2 for dose rationale), dose adjustments based on pediatric data may be needed. Therefore, a higher or lower dose will be explored in Cohort 2. If adequate exposures are achieved in Cohort 1 with no safety concerns, a higher dose that is not expected to exceed safe exposures in nonclinical studies and clinical studies may still be explored in Cohort 2 to evaluate the safety and PK of EDP-938 across a dose range. Additional cohorts in Part 1 may be added, as needed. Following completion of Part 1 for a specific age group and based on SSC review, enrollment in Part 2 for that same age group may begin.

In Part 2, subjects will be randomized 4:1 to EDP-938:placebo. Part 2 doses will be selected based on review of Part 1 data and will enable better characterization of the clinical efficacy of EDP-938. The key antiviral activity assessment will be the daily change in RSV shedding in nasal swab samples determined using RT-qPCR from Baseline through the treatment phase. The AUC for RSV RNA viral load quantitation by nasal swab while on treatment and during the follow-up visits (up to Day 14) will be assessed in this study. The use of RSV RNA viral load AUC as the assessment of antiviral activity has been previously employed in this setting, including the EDP 938-101 adult human challenge study (Section 1.4).

The eligible population comprises hospitalized or non-hospitalized individuals, who have an RSV infection. The requirement for hospitalization of subjects in Part 1 Cohort 1 Age Group 2 allows for dosing of EDP-938 to occur in a monitored and supervised environment for regular PK, clinical, and laboratory safety assessments.

At this stage of development, pediatric subjects with significant comorbidities are excluded. Similarly, the study also excludes those who are not considered to be medically stable or requiring urgent or emergency medical care. Also excluded are those with known liver, kidney, heart and/or neurologic disease.

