# 2. STUDY DESIGN

This is a Phase 2, dose-ranging, randomized, double-blind, placebo-controlled, 2-part study to evaluate the safety, tolerability, PK, clinical outcome, and antiviral activity of orally administered EDP-938 regimens in infants and children aged 28 days to 36 months with RSV-associated respiratory tract infection, who are hospitalized or non-hospitalized.

Each part of the study has 3 periods: Screening, Treatment, and Follow-up. For each subject, the duration of study will be approximately 29 days (Table 1). Study site visits and assessments are detailed in the Schedule of Assessments (SoA; Appendix 7.1).

The end of the study will be defined as the last visit of the last subject enrolled.

#### Table 1

Study Period	Duration
Screening (Day -1 to Day 1)	Up to 24 hours (note: some assessments done as part of standard of care can be used as screening assessments if they are done within 72 hours)
Treatment (Day 1 to Day 5)	5 days
Follow-up (Day 6 to Day 28)	23 days
Approximate total duration of participation	29 days maximum

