Efficacy summary tables and figures will be presented by randomized treatment group and age group for Part 1 and Part 2 separately and will be labelled as follows. Additionally, efficacy summary tables and figures for efficacy endpoints for the pooled population will be summarized using pooled data (subjects from Parts 1 and 2) as appropriate. Other summaries including disposition, analysis populations, demographics, and baseline data will be displayed by treatment group, age group for Parts 1 and 2 separately. Parts 1 and 2 will also be pooled for these summaries.

Age Group:

- " $\geq 6$  to  $\leq 36$  months"
  - $\circ$  " $\geq 6$  to <12 months"
  - $\circ$  " $\geq 12$  to  $\leq 36$  months"
- " $\geq 28$  days to <6 months"
  - $\circ$  " $\geq$ 28 days to <3 months"

 $\circ$  " $\geq$ 3 to <6 months"

Treatment:

- "EDP-938"
- "Placebo"

Study Part:

- "Part 1"
- "Part 2"
- "Parts 1 and 2"

Safety summary tables and figures will be summarized separately for Part 1 and Part 2 as well as pooled Parts 1 and 2 data by the actual treatment group. In addition, pooled Parts 1 and 2 data will be summarized by age group.

For the reporting of this study both CDISC SDTM (SDTM Implementation Guide version 3.3 or later) and ADaM (ADaM Implementation Guide version 1.1 or later) standards will be applied. A subject will be considered to have completed the study after his/her attendance at the last planned study visit (Day 28  $\pm$  4 day), or the last unscheduled visit (if any occur), as applicable. For each subject his or her study completion status (Yes/No) is recorded on the End of Study CRF.

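### The available SAP text specifies no dose or cohort column for safety or efficacy tables, although Part 1 plans at least two EDP-938 doses in each age group

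*SAP*

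**What the plan says.** **The aim.** SAP 2 describes the design as follows: "This is a Phase 2, dose-ranging, randomized, double-blind, placebo-controlled, 2-part study". Protocol 4.4 says "This study is designed to support dose selection", both within this study and for later pediatric trials. Protocol 4.4.1 adds that "this initial Phase 2 trial should identify the optimal dose and treatment duration", judged on PK, safety and antiviral activity.

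**The doses.** Protocol 4.1 plans the initial dose to "be 5 mg/kg in each age group". Protocol 4.4.1 then says of the next cohort: "Therefore, a higher or lower dose will be explored in Cohort 2". SAP 4.13.6 names final doses of 7.5 mg/kg from 12 to 36 months and 5 mg/kg below 12 months.

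**The reporting layout.**
- Efficacy (SAP 4.1): "Efficacy summary tables and figures will be presented by randomized treatment group and age group for Part 1 and Part 2 separately". The labels that follow cover age group, study part and two treatments, EDP-938 and Placebo.
- Safety (SAP 4.1): "Safety summary tables and figures will be summarized separately for Part 1 and Part 2", and for the two parts pooled, by actual treatment group. SAP 4.1 and 4.14 mention an age-group split only for the pooled parts.
- Pooled efficacy (SAP 4.13.5): EDP-938 against placebo, by age group and combined. The MMRM has a two-level treatment factor and no dose term.
- PK (SAP 4.15.1): concentrations are summarised by dose. This is the only summary in the available text that is.

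**The concern.** Part 1 contains at least two dose levels in each age group, and the stated layout puts the children on both into one EDP-938 column. Safety and tolerability are Part 1 primary endpoints, and viral-load change is a Part 1 secondary endpoint. If an adverse event, a laboratory shift or a viral response depends on dose, the column shows only the average over doses. A reader of the study report could not tell a strong effect at one dose from a weaker effect at both. Yet the protocol lists safety and antiviral activity, alongside PK, as grounds for choosing the dose.

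**Working it through.** **1. Planned numbers.** Part 1 has 12 children per cohort per age group (SAP 4.2), randomised 2:1, so 8 active and 4 placebo. Part 2 has 20 per age group, randomised 4:1, so 16 active and 4 placebo.

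- Part 1: 2 cohorts × 2 age groups × 12 = 48, of whom 32 are active and 16 placebo.
- Part 2: 2 age groups × 20 = 40, of whom 32 are active and 8 placebo.
- Total: 48 + 40 = 88, which agrees with the planned figure of approximately 90. Active 64, placebo 24.

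The SAP gives no alpha, power, effect size or SD, so there is no power statement to reproduce.

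**2. Dilution of a safety signal.** Suppose an event occurs in 3 of the 8 EDP-938 children in one dose cohort of one age group (37.5%) and in no other child on drug.

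| Display | Children on EDP-938 | Shown as |
|---|---|---|
| That dose cohort and age group alone | 8 | 3/8 = 37.5% |
| Part 1, if split by age group | 16 | 3/16 = 19% |
| Part 1, not split by age group (as SAP 4.1 and 4.14 read) | 32 | 3/32 = 9% |
| Parts 1 and 2 pooled | 64 | 3/64 = 5% |

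**3. Dilution of a viral effect.** A Part 1 efficacy column for one age group averages 8 children from each cohort. If one dose has the full effect and the other a fraction f of it, the column shows (8 × 1 + 8 × f)/16. For f = 0 this is 50% of the full effect; for f = 0.5 it is 75%.

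**4. What the other planned displays cover.**
- SAP 4.15.1 gives concentrations by dose, with no safety or efficacy outcome.
- SAP 4.15.2 plots concentration against viral load, symptom scores and the total number of TEAEs. It has no preferred terms, laboratory shifts or vital signs.
- SAP 4.13.6 repeats the viral analyses in children on the final doses. It has no safety counterpart, does not set final doses against other doses, and does not say which of the 24 planned placebo children form the comparator.
- The age labels in SAP 4.1 break at 12 months, where the final dose changes, but this does not separate doses. Children of 12 to 36 months were planned to start at 5 mg/kg in Cohort 1, and the final dose for that age is 7.5 mg/kg.

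**5. What dose columns could deliver.** Three formulas are used: the half-width of a 95% CI for a mean, t(0.975, n−1)/√n in SD units; the exact upper 95% limit for 0/n, 1 − 0.025^(1/n); and the chance of seeing a 10% event at least once, 1 − 0.9^n.

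| n on drug | CI half-width (SD) | Upper limit for 0/n | P(at least one event at 10%) |
|---|---|---|---|
| 8 | 0.84 | 36.9% | 57% |
| 16 | 0.53 | 20.6% | 81% |
| 32 | 0.36 | 10.9% | 97% |

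For scale only, assume two-sided alpha 0.05 and 80% power. The detectable difference between two doses is (1.96 + 0.84) × √(1/n + 1/n), which is 1.40 SD for 8 against 8 and 0.99 SD for 16 against 16.

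**The case against.** A reader might infer that the trial cannot show any dose relation or support its dose choice. The documents do not support that. Concentrations are tabulated by dose, the exposure-response plots include TEAEs as well as viral load, and the final-dose analyses cover the main viral endpoints. In-study doses are chosen by the steering committee from blinded safety, tolerability and PK data (Protocol 4.2.1 and 4.3), and the IDMC sees unblinded safety data. Neither waits for the final tables, and a table layout does not stop the data being split by dose later.

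Nor can it be said that no table will show a dose contrast. SAP 1 places the table shells in a separate document, and SAP 4.13.7, to which SAP 4.13.5 refers, is not in the available text. The two treatment labels are attached to the efficacy sentence; for safety the SAP says only actual treatment group.

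Dose columns would also be weak evidence. Cohorts are enrolled in sequence, and children are randomised to drug or placebo within a cohort, not between doses. Cohort 1 of Age Group 2 is hospitalised only, while Cohort 2 is mixed. Even 0/8 against 3/8 is compatible with chance: the one-sided Fisher p is 56/560 = 0.10 and the two-sided p is 0.20.

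A reader might also attach the phrase on treatment duration in Protocol 4.4.1, since the planned arms all run 5 days. That is a separate matter of rationale wording and carries no weight here.

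These objections limit what dose columns can prove. They do not explain why safety and viral-load results are reported without dose when concentrations are reported by it.

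**Conclusion.** The point holds as a reporting gap. No part of the available SAP specifies a safety or efficacy table by dose or cohort, and the MMRM has no dose term. The existing displays inform dose only in part; none gives adverse events by term, laboratory shifts, vital signs or viral-load change by dose.

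In the illustration, 37.5% at one dose in one age group becomes 9% in the Part 1 EDP-938 column, or 19% if that table is split by age group. A viral effect confined to one of two doses would be shown at half its size. These figures assume the planned cohort sizes and one dose per cohort in each age group; the doses and numbers actually used in Cohort 2 are not given. The event pattern is hypothetical.

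The gap invalidates no planned analysis. It is a worthwhile, inexpensive improvement, subject to checking whether the shells already contain a dose split.

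**What to change.** In SAP 4.1, define treatment columns by EDP-938 dose received, all EDP-938, and placebo. Apply them to adverse events, laboratory data, vital signs, viral-load change and viral-load AUC, in Part 1 and in the pooled parts. Show them within age group as well, because the final doses differ by age and a pooled dose column would otherwise mix dose with age. Label them descriptive, with a note that cohorts were sequential and that Cohort 1 of Age Group 2 was hospitalised only. In SAP 4.13.6, state which placebo children are the comparator. If the shells already have a dose split, a cross-reference in SAP 4.1 is enough.

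The cost is extra table columns from data already held, and cells of about 8 children that need cautious reading. The change should be made before unblinding, the limit that Protocol 11.2 sets for SAP changes.

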# 4.2 Sample Size Considerations

No formal hypothesis testing is planned for Parts 1 or 2 of this study. Therefore, no formal sample size justification is provided. Approximately 90 subjects will participate in this study: 12 subjects are planned in each cohort of the age groups in Part 1 (24 subjects in each age group). In Part 2, 20 subjects are planned in each of the age groups. Additional subjects may be added based on SSC recommendations.

# 4.3 Handling of Dropouts or Missing Data

In general, missing data will not be imputed and all summary statistics will be reported based upon observed data. In particular, incomplete dates for adverse events and concomitant medication use (*Section 4.3.1*) are presented. For any other data which has partial dates, which are required for use in time related calculations, these dates will be completed using a suitably conservative approach. Dates will be shown in subject listings as they have been recorded.

# 4.3.1 Missing Dates

Imputation rules for missing or partial AE start/end dates are defined as:

- Only Day of AE start date is missing:
  - $\circ$   $\,$  If the AE start year and month are the same as that for the first dose date, then:

- If the full (or partial) AE end date is NOT before the first dose date or AE end date is missing, then impute the AE start day as the day of first dose date.
- Otherwise, impute the AE start day as 1.
- If Day and Month of AE start date are missing:
  - If AE start year = first dose year, then:
    - If the full (or partial) AE end date is NOT before the first dose date or AE end date is missing, then impute the AE start Month and Day as the Month and Day of first dose date.
    - If the full (or partial) AE end date is before the first dose date, then impute the AE start Month and Day as the Month and Day of AE end date after imputation.
  - If AE start date > first dose year, impute the AE start MONTH as January and the DAY as 1.
  - If AE start year < first dose year, then:
    - If the full (or partial) AE end date is NOT before the 31st of December of AE start year, or AE end date is missing, then impute the AE start MONTH as December and the DAY as 31.
    - Otherwise, if the full (or partial) AE end date is before the 31st of December and AE start year, then impute the AE start Month and Day as the Month and Day of AE end date after imputation.
- If Year of AE start date is missing:
  - If the year of AE start is missing or AE start date is completely missing, then query site and leave as missing.
- For missing and partial adverse event end dates, imputation will be performed as follows:
  - If only the day of the month is missing, the last day of the month will be used to replace the missing day.
  - If the day and month are missing or a date is completely missing, it will be considered as missing.

Imputation rules for missing or partial medication start/stop dates are defined below:

- If only Day of CM start date is missing:
  - If the CM start year and month are the same as that for the first dose date, then:
    - If the full (or partial) CM end date is NOT before the first dose date or CM end date is missing, then impute the CM start day as the day of first dose date.
  - Otherwise, impute the CM start day as 1.
- If Day and Month of CM start date are missing:
  - If CM start year = first dose year, then:

- If the full (or partial) CM end date is NOT before the first dose date or CM end date is missing, then impute the CM start Month and Day as the Month and Day of first dose date.
- If the full (or partial) CM end date is before the first dose date, then impute the CM start Month and Day as the Month and Day of CM end date after imputation.
- If CM start date > first dose year, impute the CM start MONTH as January and the DAY as 1.
- If CM start year < first dose year, then:
  - If the full (or partial) CM end date is NOT before the 31st of December of CM start year, or CM end date is missing, then impute the CM start MONTH as December and the DAY as 31.
  - Otherwise, if the full (or partial) CM end date is before the 31st of December and CM start year, then impute the CM start Month and Day as the Month and Day of CM end date after imputation.
- If Year of CM start date is missing:
  - If the year of CM start is missing or CM start date is completely missing, then query site and leave as missing.
- For missing and partial CM end dates, imputation will be performed as follows:
  - If only the day of the month is missing, the last day of the month will be used to replace the missing day.
  - If the day and month are missing or a date is completely missing, it will be considered as missing.

# 4.4 Analysis Populations

- *Safety (SAF) Population*: All subjects who receive any dose (including partial doses) of any study drug;
- *PK Population*: All subjects who receive one full dose of study drug and have blood samples with quantifiable plasma levels to allow estimation of PK parameters;
- *Efficacy Population*: All subjects who receive one full dose of study drug.
- *Modified Intention to Treat 3 (mITT-3) population*: All subjects who receive one full dose of study drug and have onset of the first sign of respiratory infection within 3 days before randomization.
- Modified Intention to Treat 5 (mITT-5) population: All subjects who receive one full dose of study drug and have onset of the first sign of respiratory infection within 5 days before randomization.

